Title: Cooking for Health

Trial registration: This study was registered on ClinicalTrials.gov on October 9, 2018 with Identifier NCT03699709.

Version: 06/07/22

Purpose/Rationale:

The purpose of the Cooking for Health Study is to develop a distance-learning-based culturally-adapted healthy food budgeting, purchasing, and cooking intervention, adapted from Cooking Matters®, for American Indian (AI) adults with type 2 diabetes who reside in an AI community in South Dakota, and to test the efficacy of the intervention on: (1) change (from baseline) in self-reported intake of sugar-sweetened beverages (SSBs); and (2) change (from baseline) in the frequency of healthy and unhealthy food purchases.

Methods/Design:

Study design

The Cooking for Health Study is a randomized controlled trial (RCT), which will enroll 165 AIs who reside in a reservation community in South Dakota. Participants will be randomized to a 12-month intervention or control arm using a 1:1 randomization scheme. Participants in the intervention arm will complete a 12-month curriculum, which includes 12 distance-learning lessons (i.e., both paper material and videos) related to healthy food budgeting, purchasing, and cooking skills. Participants in the control arm will receive access to the intervention materials at the end of the study. All study participants will attend three in-person study visits for data collection at baseline (month 0), month 6 and month 12.

Study population

AI men and women 18+ years old with a physician-diagnosis of type 2 diabetes[17] who reside on the reservation or in a border town and self-report doing most of their household's food shopping and meal preparation will be eligible to participate in the study. Only one person per household will be eligible to participate to avoid non-independence of food choices and potential cross-arm contamination. Individuals who are pregnant, have a history of bariatric surgery, are on dialysis (or with underlying chronic kidney disease), or are cognitively impaired will be excluded from participation as these conditions may influence diet or ability to engage with the intervention. Additionally, individuals without a reliable place to cook or store food (e.g., homeless) will be ineligible to participate.

Curriculum Development

The Cooking for Health Study used Cooking Matters® as a foundation for intervention development. Investigators planned to: (1) modify and supplement the curriculum to use a distance-learning platform (versus standard in-person delivery) to maximize reach in a resource-limited setting; (2) implement a more comprehensive and longer-term curriculum (12 months rather than six weeks used by Cooking Matters®); and (3) focus on adults with type 2 diabetes (versus families with school-aged children, the current population on which Cooking Matters® focuses). However, focus groups with community members highlighted the need for more substantial adaptations to the curriculum. Further adjustments included: (1) a greater focus on food budgeting and meal planning for multi-generational families with limited budgets, including how to most effectively use government assistance, such as the Food Distribution Program on Indian Reservations (FDPIR), commonly known as commodity foods, or SNAP; (2) incorporation of healthy, traditional and locally available foods into the curriculum and recipes; (3) more detailed instruction on unit pricing, particularly for individuals with low literacy and numeracy skills; (4) focusing the curriculum on the ADA consensus recommendations for effective diabetes nutrition for management of type 2 diabetes, including limiting unhealthy

food and SSBs [12]; (5) food safety, including proper storage of fresh and frozen fruits, vegetables, and meats; and (6) the incorporation of culturally meaningful language, art, and photos throughout the curriculum. All modifications were made following the stages of cultural adaptation, as described by Barrera and Castro[18].

Informed consent

All research activities were approved by the University of Washington Institutional Review Board (IRB), the Indian Health Services Great Plains Area IRB, and the tribal health board. Study staff will obtain written informed consent from all study participants before data collection at their first study visit. Study staff will describe all study procedures and the risks and benefits of participation. Study staff will inform potential participants that participation in the study is voluntary, and participants may withdraw at any time. After study staff have addressed any questions or concerns, they will ask the participant to sign the consent form.

In-person study visits

All study participants will complete in-person study visits at baseline, month 6, and month 12 at the study field site on the reservation. Each in-person study visit includes a personal interview, a physical exam, fasting blood draw, and completion of several questionnaires to ascertain usual (i.e., past six months) diet and other diet-related behaviors (e.g. frequency of healthy and unhealthy food purchases, cooking confidence, food resource management, and household food shopping habits). During months 6 and 12, a random subsample of participants in the intervention arm (n=30) will partake in semi-structured interviews.

Randomization

Investigators will generate a 1:1 randomization sequence using a permuted block design with concealed blocks of variable size. Investigators will provide study staff with sequentially numbered sealed opaque envelopes that contain treatment assignment. After each participant's baseline data is collected, study staff will open the next-in-order sealed envelope to determine the participant's arm assignment (i.e., intervention or control).

Intervention materials

After randomization, participants assigned to the intervention arm will receive all intervention materials, including a binder with all paper materials (i.e., lesson handouts, recipes), a username and password to access videos on Canvas®, and a reusable shopping bag with several tools intended to enhance engagement with the study materials (i.e., calculator, measuring cup set for dry and liquid ingredients, measuring spoon set, stirring/cooking spoons, rubber scraper, turner, whisk, cutting board, knife set, and CalorieKing© Book). Participants randomized to the control arm will receive these materials at the end of the study.

Outcomes

The effect of the intervention on change (from baseline) in self-reported intake of SSBs and frequency of healthy and unhealthy food purchases are the primary outcomes of interest.

Statistical Analyses Plan

Intent-to-treat analyses will estimate the effect of the intervention on all outcomes of interest, compared to control, longitudinally across groups using general linear models.

Data management

REDCap®, a secure web application for building and managing online surveys and databases, will be used for data capture of all questionnaires using password-protected computers[32]. All data will be transferred, encrypted, and backed-up daily, except the food frequency questionnaire—which will be sent to the Fred Hutchinson Cancer Research Center (Seattle, WA) for analysis.

Data safety monitoring

Investigators will provide study oversight, ensure that the trial is conducted according to the study protocol, and will be responsible for the data and safety monitoring by ensuring the safety of all participants. As the risks of participating in the study are minimal, we do not anticipate numerous adverse events (AEs). All AEs will be reported according to the UW Institutional Review Board (IRB) and the Great Plains Area Indian Health Services IRB.

Discussion:

There is a critical need to develop novel, targeted, and sustainable interventions to promote healthy diet in rural AI communities. In partnership with the community, the work described herein will develop and test the effect of a culturally-adapted intervention to improve diet among AIs with type 2 diabetes. If successful, the intervention can be tailored to other rural and underserved communities. The results of this study will also inform further efforts to design and implement diet interventions in AI communities or other resource-limited settings.

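### Do semi-structured interviews held only with 30 intervention participants compromise the comparison of the self-reported primary outcomes?

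*Combined protocol and SAP*

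**What the plan says.** The section on in-person study visits describes two kinds of interview. One is part of every visit for everyone: "Each in-person study visit includes a personal interview, a physical exam, fasting blood draw, and completion of several questionnaires". The other is extra and selective: during months 6 and 12, "a random subsample of participants in the intervention arm (n=30) will partake in semi-structured interviews". Both arms attend on the same schedule ("All study participants will complete in-person study visits at baseline, month 6, and month 12 at the study field site on the reservation"), so the selective interviews fall in the same months as the two post-baseline assessments. The diet questionnaires ask about the preceding six months.

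The Outcomes section names "change (from baseline) in self-reported intake of SSBs and frequency of healthy and unhealthy food purchases are the primary outcomes of interest". The Statistical Analyses Plan is one sentence: intent-to-treat for all outcomes, "longitudinally across groups using general linear models". It does not mention the interviews.

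Three details are not given: the order of interview and questionnaires within a visit, whether one set of 30 is used at both months, and when the set is drawn.

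**The concern.** A contact that only one arm receives, close to the measurement of a self-reported outcome, can change what people report without changing what they do. Intervention participants know their allocation because they hold the binder, the video login and the kitchen tools. A conversation just before the questionnaires might encourage more favourable answers at that visit. Even if it follows the month-6 questionnaires, a month-6 interview stands at the start of the six-month period that the month-12 diet questionnaire covers, so it might carry over.

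Any such effect would be counted with the effect of the distance-learning curriculum, which is what the trial sets out to test. Intent-to-treat keeps the interviewees in the comparison but cannot separate the two sources. If the effect were large, the curriculum could look better (or worse) than it is.

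**Working it through.** The plan has no figure to reproduce here. The 30 is stated without derivation, and no alpha, power, SD or dropout is given. The steps below ask how far an interview effect could reach and whether an added analysis would reveal it.

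**Inputs.** From Study design: 165 participants randomised 1:1, so 82 or 83 per arm. From In-person study visits: 30 interviewees, intervention arm only. Assumed: two-sided alpha 0.05, common SD, complete data, and an interview effect of x SD in each interviewee.

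**Step 1: share of the arm.**
- One set of 30: 30/83 = 0.361; 30/82 = 0.366.
- Thirty in total, split evenly over the two months: 15/83 = 0.181 at each.
- A different 30 at each month: 60/83 = 0.723; 60/82 = 0.732.

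If questionnaires come first, only month-6 interviewees can be affected at month 12, so the exposed share there is at most about 0.36 under every reading. The 0.72 figure needs both a fresh 30 at month 12 and interviews held before the questionnaires.

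**Step 2: effect on the comparison.** Shift in arm mean = share × x, so about 0.36x at month 12 with 30 exposed. If months 6 and 12 were averaged equally and the month-6 interview came after the questionnaires, it would be 0.36x/2 = 0.18x.

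**Step 3: illustration with no true curriculum effect.** SE of the arm difference = √(1/83 + 1/82) = 0.156 SD. Rejection probability = Φ(shift/SE − 1.96) + Φ(−shift/SE − 1.96). With 30 of 82 interviewed:

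| Assumed x (SD) | Shift (SD) | Rejection rate |
|---|---|---|
| 0 | 0 | 5.0% |
| 0.1 | 0.037 | 5.6% |
| 0.2 | 0.073 | 7.6% |
| 0.3 | 0.110 | 10.9% |
| 0.5 | 0.183 | 21.7% |

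On the 60-person, interview-first reading, x = 0.2 gives a shift of 0.146 SD and a rate of 15.6%. None of these values of x comes from the documents.

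**Step 4: what leaving out the 30 would show.**
- SE without the 30: √(1/53 + 1/82) = 0.176 SD, which is 0.1762/0.1557 = 1.13 times the full-sample SE.
- SE of interviewed versus not interviewed within the arm: √(1/30 + 1/53) = 0.228 SD.
- With unadjusted means, the gap between the full and reduced estimates equals 30/83 times that within-arm difference, so its SE is 0.361 × 0.228 = 0.083 SD.
- x at which the expected gap reaches 1.96 of its SEs: 1.96 × 0.228 = 0.45 SD.
- x detectable with 80% power (assumed): 2.80 × 0.228 = 0.64 SD.

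At x = 0.2 the expected gap is 0.361 × 0.2 = 0.072 SD, less than one SE.

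**The case for a change.** The best case for acting is that it costs little. The extra contact is in one arm, participants are not blinded, and the outcomes are self-reported. Fixing the visit order, recording the list of 30 and writing one sensitivity analysis would need no further visits or participants. Holding interviews last would remove same-visit influence, and excluding everyone on the list, interviewed or not, would avoid selecting on attendance.

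The factual part stands: order and re-use of the 30 are not stated, and intent-to-treat does not remove a reporting effect. The rest carries less weight. The sampling frame is given at arm level, and drawing from all participants randomised to the intervention is its natural reading; nothing suggests volunteers. Doing the questionnaires before a long conversation is the order field staff would sensibly adopt. Neither the content nor the purpose of the interviews is described, so nothing shows that they would alter reported intake or purchases. Both arms already have a personal interview and diet questionnaires at every visit, so the one-sided contact is one or two conversations on top of a 12-month curriculum. The six-month recall period shows that carry-over is possible, not that it happens. The proposed analysis would leave the primary result as it is and, by step 4, could neither confirm nor exclude a small effect.

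**Conclusion.** No change to the plan is needed. This is missing procedural detail that competent staff and analysts would fill sensibly; no stated rule produces a wrong result. The exposed share is 36-37% of the intervention arm if one set of 30 is used, and 72-73% only if 60 different people are interviewed and the interviews come first. The resulting bias is that share times an effect whose size and direction the documents do not give and which may be nil. The primary intent-to-treat analysis is the same either way, and a sensitivity analysis without the 30 would have 80% power only for an interview effect of about 0.64 SD. The power and error figures assume two-sided alpha 0.05, a common SD and no dropout.

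### The analysis sentence names no baseline adjustment and no primary visit for outcomes defined as change from baseline; if baseline is not adjusted for, precision is given up (standard error about 8-16% larger than it need be is avoided by adjustment, under stated assumptions)

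*Combined protocol and SAP*

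**What the plan says.** The Statistical Analyses Plan is a single sentence: "Intent-to-treat analyses will estimate the effect of the intervention on all outcomes of interest", "compared to control, longitudinally across groups using general linear models". It says nothing about how the baseline value enters (as covariate, subtracted, or as part of the response), which visit or contrast is primary, or what within-person covariance is used. No other section adds to it.

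The Outcomes section states that "change (from baseline) in self-reported intake of SSBs and frequency of healthy and unhealthy food purchases are the primary outcomes of interest", with no visit attached. Study design provides for "three in-person study visits for data collection at baseline (month 0), month 6 and month 12", so there are two follow-up values to choose from or combine.

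Under Randomization, after each participant's "baseline data is collected, study staff will open the next-in-order sealed envelope". The baseline value therefore precedes assignment and should be available for everyone randomised. Under In-person study visits, each visit includes "questionnaires to ascertain usual (i.e., past six months) diet".

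**The concern.** Two things are left open.

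**Baseline.** An outcome defined as change from baseline is naturally read as a simple difference, follow-up minus baseline, compared between arms. That is valid in a randomised trial. In large samples, however, it is never more precise than comparing follow-up values adjusted for baseline, and it is usually less precise. The baseline value is already collected before randomisation, so in a trial of 165 people any loss of precision is avoidable.

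**Visit.** The month-6, month-12 and averaged effects are different quantities. This is clearest for sugar-sweetened beverage (SSB) intake. The diet questionnaire looks back six months, so month 6 describes months 0-6 of the 12-month curriculum and month 12 describes months 6-12. The recall period for food purchases is not clearly stated, so this argument is confined to the diet outcome. For every primary outcome, though, leaving the visit unnamed means that the claimed effect could be settled after the results are seen.

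**Working it through.** **Inputs from the documents.** N = 165, 1:1 allocation, visits at months 0, 6 and 12, baseline collected before assignment. No correlation, SD, alpha, power or dropout is given, so there is no stated figure to reproduce.

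**Assumptions.** Correlation r between baseline and month 12 of 0.4-0.7; k = baseline SD / month-12 SD of 0.8, 1 or 1.25; one visit; no missing values.

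**Formula.** In units of the month-12 variance, the per-person variance is:
- unadjusted change score: 1 + k² − 2rk
- baseline-adjusted value: 1 − r²

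So the SE ratio (adjusted / change score) = √[(1 − r²)/(1 + k² − 2rk)], which is √[(1 + r)/2] when k = 1. Example: r = 0.4, k = 1 gives √(0.84/1.20) = 0.837, a 16.3% reduction. The number of people that an unadjusted change score would need for the same precision is 165/ratio², here 165/0.70 = 236.

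SE ratio, with equivalent N in brackets:

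| r | k = 0.8 | k = 1 | k = 1.25 |
|---|---|---|---|
| 0.4 | 0.917 (196) | 0.837 (236) | 0.733 (307) |
| 0.5 | 0.945 (185) | 0.866 (220) | 0.756 (289) |
| 0.6 | 0.970 (175) | 0.894 (206) | 0.776 (274) |
| 0.7 | 0.990 (168) | 0.922 (194) | 0.792 (263) |

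Equal SDs thus give a reduction of 7.8-16.3%. Across k = 0.8-1.25 the range is 1.0% (r = 0.7, k = 0.8) to 26.7% (r = 0.4, k = 1.25).

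**Simulation check** (20,000 null trials of 83/82 per setting, r = 0.4, 0.5, 0.6, 0.7). Normal data with equal SDs gave SE ratios of 0.842, 0.863, 0.895 and 0.919. Right-skewed data (log-normal, log SD 0.8, r on the log scale) gave 0.809, 0.830, 0.857 and 0.889. Type I error of both methods stayed between 0.044 and 0.053 at a nominal 0.05.

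**Cost of the covariate.** One degree of freedom inflates the SE by about √(1 + 1/161) = 1.003. With k = 1 the reductions become 16.1% (r = 0.4) and 7.5% (r = 0.7).

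**If baseline is part of the response.** A longitudinal model with a common baseline mean has the same month-12 SE as the adjusted analysis (ratio 1.000 for r = 0.4-0.7), so there is nothing to gain. With baseline means free by arm it matches the change score, and the table applies.

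**Unnamed visit, as a conditional illustration.** Suppose both visits were tested at an assumed two-sided 5% level and either result could be claimed. For one outcome, with correlation 0.3, 0.4, 0.5, 0.6, 0.7 or 0.8 between the two changes, the chance of at least one false positive is 9.5%, 9.3%, 9.1%, 8.7%, 8.3% or 7.8%.

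**The case against.** The strongest reply is that the plan does not prescribe an unadjusted change score. Defining the outcome as change from baseline does not exclude a baseline covariate, and a longitudinal general linear model can be one that already captures the whole gain. This stands. The precision loss is conditional on the model eventually used, and 8-16% cannot be stated as a fact about this trial. Nor can equal SDs be presumed for a behaviour that the intervention aims to change, which is why the wider range is shown.

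The omission survives the reply. The sentence fits the efficient model and the inefficient one equally well, and says nothing that decides between them.

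A reader might go further and infer that the sentence commits the trial to an invalid analysis: treating a person's two follow-up changes as independent rows, or testing both visits and reporting the better one. The documents do not support this. They specify no such pooling and no such selection, and they state no significance level. The 7.8-9.5% figures show what an unnamed visit could permit, not what is planned.

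It can also be said that a 12-month curriculum already implies month 12. That is a reasonable inference, but the text does not state it, and an averaged effect would also be legitimate.

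**Conclusion.** The point holds in conditional form. The plan fixes neither the baseline adjustment nor the primary visit, and the baseline value is available before randomisation. If the analysis is an unadjusted change score, or a longitudinal model with arm-specific baseline means, adjustment would cut the month-12 standard error by about 8-16% (equal SDs, assumed correlation 0.4-0.7), or about 1-27% if the SD ratio is 0.8-1.25. If baseline means are already constrained to be equal, the gain is about zero. The direction is secure in large samples; the size rests on figures that the documents do not give.

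This is an available improvement to a plan that allows a valid analysis, together with a primary effect that is not fixed in advance. It is not evidence of a wrong analysis. It should be fixed because the remedy is small and the unnamed visit affects every primary outcome.

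**What to change.** Replace the analysis sentence, for the primary outcomes, with text to this effect:

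*Each primary outcome is compared between arms at month 12, adjusted for the baseline value of that outcome, from a REML repeated-measures model of the month-6 and month-12 values. Fixed effects are arm, visit, arm-by-visit, baseline and baseline-by-visit; the within-person covariance is unstructured. Every randomised participant with a follow-up value is included in the randomised arm. The number with no follow-up value is reported by arm.*

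- **Visit.** Month 12, the end of the curriculum, is the natural choice, but the choice is the investigators'. What matters is that one visit or contrast is named in advance.
- **Baseline-by-visit.** This lets the baseline slope differ between visits. With assumed baseline correlations of 0.7 (month 6) and 0.4 (month 12) and 0.6 between the follow-up visits, forcing one slope makes the month-12 SE about 2.8% larger; with 0.6, 0.4 and 0.6 it is about 0.9% larger.
- **Simpler alternative.** A baseline-adjusted linear model of the month-12 value alone is acceptable. With an assumed 15% monotone withdrawal, half of it by month 6, and compound symmetry, the repeated-measures model carries month-12 information worth 141-142 people, against 140 (165 × 0.85) with a month-12 value. The gain comes from the baseline covariate, not from recovering missing participants.

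The cost is a change of wording, a few lines of standard code, and one or two degrees of freedom. No new data, participants or staff are needed.
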